10.3.1. Definition of AE

AE Definition

 • An AE is any untoward medical occurrence in a clinical study participant, temporally associated with the use of a study intervention, whether considered related to the study intervention. • NOTE: An AE can therefore be any unfavorable and unintended sign (including an abnormal laboratory finding), symptom, or disease (new or exacerbated) temporally associated with the use of a study intervention.

Events Meeting the AE Definition

 • Any abnormal laboratory test results (hematology, clinical chemistry, or urinalysis) or other safety assessments (e.g., ECG, radiological scans, vital signs measurements), including those that worsen from baseline, considered clinically significant in the medical and scientific judgment of the investigator (i.e., not related to progression of underlying disease). • Exacerbation of a chronic or intermittent pre-existing condition including either an increase in frequency and/or intensity of the condition. • New conditions detected or diagnosed after study intervention administration even though it may have been present before the start of the study. • Signs, symptoms, or the clinical sequelae of a suspected drug-drug interaction. • Signs, symptoms, or the clinical sequelae of a suspected overdose of either study intervention or a concomitant medication. Overdose per se will not be reported as an AE/SAE unless it is an intentional overdose taken with possible suicidal/self-harming intent. Such overdoses should be reported regardless of sequelae. • "Lack of efficacy" or "failure of expected pharmacological action" per se will not be reported as an AE or SAE. Such instances will be captured in the efficacy assessments. However, the signs, symptoms, and/or clinical sequelae resulting from lack of efficacy will be reported as AE or SAE if they fulfil the definition of an AE or SAE.

Events NOT Meeting the AE Definition

 • Any clinically significant abnormal laboratory findings or other abnormal safety assessments which are associated with the underlying disease, unless judged by the investigator to be more severe than expected for the participant's condition.

- The disease/disorder being studied or expected progression, signs, or symptoms of the disease/disorder being studied, unless more severe than expected for the participant's condition.
- Medical or surgical procedure (e.g., endoscopy, appendectomy): the condition that leads to the procedure is the AE.
- Situations in which an untoward medical occurrence did not occur (social and/or convenience admission to a hospital).
- Anticipated day-to-day fluctuations of pre-existing disease(s) or condition(s) present or detected at the start of the study that do not worsen.

10.3.2. Definition of SAE

If an event is not an AE per definition above, then it cannot be an SAE even if serious conditions are met (e.g., hospitalization for signs/symptoms of the disease under study, death due to progression of disease).

A SAE is defined as any untoward medical occurrence that, at any dose:	
Results in death	
Is life-threatening	
The term 'life-threatening' in the definition of 'serious' refers to an event in which the participant was at risk of death at the time of the event. It does not refer to an event, which hypothetically might have caused death, if it were more severe.

Requires inpatient hospitalization or prolongation of existing hospitalization	
 • In general, hospitalization signifies that the participant has been detained (usually involving at least an overnight stay) at the hospital or emergency ward for observation and/or treatment that would not have been appropriate in the physician's office or outpatient setting. Complications that occur during hospitalization are AE. If a complication prolongs hospitalization or fulfils any other serious criteria, the event is serious. When in doubt as to whether "hospitalization" occurred or was necessary, the AE should be considered serious. • Hospitalization for elective treatment of a pre-existing condition that did not worsen from baseline is not considered an AE.
Results in persistent or significant disability/incapacity	
 • The term disability means a substantial disruption of a person's ability to conduct normal life functions. • This definition is not intended to include experiences of relatively minor medical significance such as uncomplicated headache, nausea, vomiting, diarrhea, influenza, and accidental trauma (e.g. sprained ankle) which may interfere with or prevent everyday life functions but do not constitute a substantial disruption.

Is a congenital anomaly/birth defect**Other situations:**

- Medical or scientific judgment should be exercised in deciding whether SAE reporting is appropriate in other situations such as important medical events that may not be immediately life-threatening or result in death or hospitalization but may jeopardize the participant or may require medical or surgical intervention to prevent one of the other outcomes listed in the above definition. These events should usually be considered serious.
- Examples of such events include invasive or malignant cancers, intensive treatment in an emergency room or at home for allergic bronchospasm, blood dyscrasias or convulsions that do not result in hospitalization, or development of drug dependency or drug abuse.

10.3.3. Definition of Cardiovascular Events**Cardiovascular Events (CV) Definition:**

Investigators will be required to record the CV in the CRF within one week of occurrence for the following AEs and SAEs:

- Myocardial infarction/unstable angina
- Congestive heart failure
- Arrhythmias
- Valvulopathy
- Pulmonary hypertension
- Cerebrovascular events/stroke and transient ischemic attack
- Peripheral arterial thromboembolism
- Deep venous thrombosis/pulmonary embolism
- Revascularization

10.3.4. Recording and Follow-Up of AE and SAE**AE and SAE Recording**

- When an AE/SAE occurs, it is the responsibility of the investigator to review all documentation (e.g. hospital progress notes, laboratory, and diagnostics reports) related to the event.
- The investigator will then record all relevant AE/SAE information in the CRF.

- It is **not** acceptable for the investigator to send photocopies of the participant's medical records to GSK in lieu of completion of the GSK /AE/SAE CRF page.
- There may be instances when copies of medical records for certain cases are requested by GSK. In this case, all participant identifiers, with the exception of the participant number, will be redacted on the copies of the medical records before submission to GSK.
- The investigator will attempt to establish a diagnosis of the event based on signs, symptoms, and/or other clinical information. Whenever possible, the diagnosis (not the individual signs/symptoms) will be documented as the AE/SAE.

Assessment of Intensity

The investigator will make an assessment of intensity for each AE and SAE reported during the study and assign it to 1 of the following categories:

- Mild: An event that is easily tolerated by the participant, causing minimal discomfort and not interfering with everyday activities.
- Moderate: An event that causes sufficient discomfort and interferes with normal everyday activities.
- Severe: An event that prevents normal everyday activities. An AE that is assessed as severe should not be confused with an SAE. Severe is a category utilized for rating the intensity of an event; and both AE and SAE can be assessed as severe.
An event is defined as 'serious' when it meets at least 1 of the predefined outcomes as described in the definition of an SAE, NOT when it is rated as severe.
Other measures to evaluate AE and SAE may be utilized (e.g., [NCI-CTCAE v5](#)).

Assessment of Causality

- The investigator is obligated to assess the relationship between study intervention and each occurrence of each AE/SAE.
- A "reasonable possibility" of a relationship conveys that there are facts, evidence, and/or arguments to suggest a causal relationship, rather than a relationship cannot be ruled out.
- The investigator will use clinical judgment to determine the relationship.
- Alternative causes, such as underlying disease(s), concomitant therapy, and other risk factors, as well as the temporal relationship of the event to study intervention administration will be considered and investigated.
- The investigator will also consult the IB and/or Product Information, for marketed products, in his/her assessment.
- For each AE/SAE, the investigator **must** document in the medical notes that he/she has reviewed the AE/SAE and has provided an assessment of causality.

- There may be situations in which an SAE has occurred, and the investigator has minimal information to include in the initial report to GSK. However, **it is very important that the investigator always make an assessment of causality for every event before the initial transmission of the SAE data to GSK.**
- The investigator may change his/her opinion of causality in light of follow-up information and send an SAE follow-up report with the updated causality assessment.
- The causality assessment is one of the criteria used when determining regulatory reporting requirements.

Follow-up of AE and SAE

- The investigator is obligated to perform or arrange for the conduct of supplemental measurements and/or evaluations as medically indicated or as requested by GSK to elucidate the nature and/or causality of the AE or SAE as fully as possible. This may include additional laboratory tests or investigations, histopathological examinations, or consultation with other health care professionals.
- New or updated information will be recorded in the originally completed CRF.
- The investigator will submit any updated SAE data to GSK within 24 hours of receipt of the information.

10.3.5. Reporting of SAE to GSK

SAE Reporting to GSK via Electronic Data Collection Tool

- The primary mechanism for reporting SAE to GSK will be the electronic data collection tool.
- If the electronic system is unavailable, then the site will use the paper SAE data collection tool (see next section) in order to report the event within 24 hours.
- The site will enter the SAE data into the electronic system as soon as it becomes available.
- The investigator or medically-qualified sub-investigator must show evidence within the eCRF (e.g., check review box, signature, etc.) of review and verification of the relationship of each SAE to IP/study participation (causality) within 72 hours of SAE entry into the eCRF.
- After the study is completed at a given site, the electronic data collection tool will be taken off-line to prevent the entry of new data or changes to existing data.
- If a site receives a report of a new SAE from a study participant or receives updated data on a previously reported SAE after the electronic data collection tool has been taken off-line, then the site can report this information on a paper SAE form (see next section) or to the medical monitor by telephone.

- Contacts for SAE reporting can be found in SRM.

SAE and AEs Leading to Study Discontinuation Reporting to GSK via Paper CRF

- If the electronic system is unavailable for greater than 24 hours, the site will use the paper SAE data collection tool and email to [contact] or fax to [contact]. Site will enter the SAE or AE data into the electronic system as soon as it becomes available unless paper SAEs and AEs leading to study discontinuation (where indicated) are being collected after DCO (below).
- The paper SAE/AE data collection tool will also be utilized for SAE and AE (where indicated) reporting after the DCO for final analysis, at which time no entry into the eCRF will be required, as the clinical database will be closed.
- In rare circumstances and in the absence of facsimile equipment, notification by telephone is acceptable with a copy of the SAE data collection tool sent by overnight mail or courier service.
- Initial notification via telephone does not replace the need for the investigator to complete and sign the SAE CRF pages within the designated reporting time frames.
- Contacts for SAE reporting can be found in SRM.

10.4. Appendix 4: Contraceptive Guidance and Collection of Pregnancy Information**10.4.1. Definitions****Woman of Childbearing Potential (WOCBP)**

A woman is considered fertile following menarche and until becoming post-menopausal unless permanently sterile (see below).

If fertility is unclear (e.g., amenorrhea in adolescents or athletes) and a menstrual cycle cannot be confirmed before first dose of study intervention, additional evaluation should be considered.

Women in the following categories are not considered WOCBP

1. Premenarchal
2. Premenopausal female with 1 of the following:
 - Documented hysterectomy
 - Documented bilateral salpingectomy
 - Documented bilateral oophorectomy

For individuals with permanent infertility due to an alternate medical cause other than the above, (e.g., Müllerian agenesis, androgen insensitivity), investigator discretion should be applied to determining study entry.

Note: Documentation can come from the site personnel's: review of the participant's medical records, medical examination, or medical history interview.

3. Postmenopausal female
 - A postmenopausal state is defined as no menses for 12 months without an alternative medical cause.
 - A high follicle stimulating hormone (FSH) level in the postmenopausal range may be used to confirm a postmenopausal state in women not using hormonal contraception or hormonal replacement therapy (HRT). However, in the absence of 12 months of amenorrhea, confirmation with more than one FSH measurement is required.
 - Females on HRT and whose menopausal status is in doubt will be required to use one of the non-estrogen hormonal highly effective contraception methods if they wish to continue their HRT during the study. Otherwise, they must discontinue HRT to allow confirmation of postmenopausal status before study enrollment

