8.5.1. Time Period and Frequency for Collecting AE and SAE Information

All SAEs will be collected from the signing of the ICF at the time points specified in the [Table 1](#). Any SAEs assessed as related to study participation (e.g., study intervention, protocol-mandated procedures, invasive tests, or change in existing therapy) or related to a GSK product will be recorded from the time a participant consents to participate in the study.

All AEs will be collected from the signing of the ICF at the time points specified in [Table 1](#). Medical occurrences that begin before the start of study intervention but after obtaining informed consent will be recorded on the Medical History/Current Medical Conditions section of the case report form (CRF) not the AE section.

- All SAEs will be recorded and reported to the sponsor or designee immediately and under no circumstance should this exceed 24 hours, as indicated in [Appendix 3](#). The investigator will submit any updated SAE data to the sponsor within 24 hours of it being available.
- Investigators are not obligated to actively seek AEs or SAEs after the conclusion of the study participation. However, if the investigator learns of any SAE, including a death, at any time after a participant has been discharged from the study, and he/she considers the event to be reasonably related to the study intervention or study participation, the investigator must promptly notify the sponsor.

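### Section 10.3.5 gives two conflicting triggers for the paper SAE back-up, and the more-than-24-hours trigger does not fit the absolute 24-hour limit in Section 8.5.1

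*Protocol*

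**What the plan says.** Protocol Section 8.5.1 sets the limit for SAEs: they are to be reported "immediately and under no circumstance should this exceed 24 hours". It gives no exception for a system outage.

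Protocol Section 10.3.5 then describes two reporting routes in two consecutive blocks.

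- The electronic-tool block names the electronic system as the primary route. If it cannot be used, "then the site will use the paper SAE data collection tool (see next section) in order to report the event within 24 hours". No minimum length of outage is stated.
- The paper-CRF block is the section to which that sentence refers, and it carries the email and fax instructions. It opens with: "If the electronic system is unavailable for greater than 24 hours, the site will use the paper SAE data collection tool".

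The paper-CRF block also allows telephone notification in rare circumstances where no fax equipment is available. It adds the caution that "Initial notification via telephone does not replace the need for the investigator to complete and sign the SAE CRF pages" on time. On the period after the data cut-off (DCO) it says: "The paper SAE/AE data collection tool will also be utilized for SAE and AE (where indicated) reporting after the DCO for final analysis".

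**The concern.** The same form has two different triggers in the same section, and nothing in the text says which prevails. During an outage, a site that follows the cross-reference from the first block arrives at the block with the longer condition, and that is where the practical instructions are.

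A back-up whose trigger is an outage longer than 24 hours does not fit a rule whose outer limit is 24 hours. If a site works from the paper-CRF block, a report can pass the limit while the site is following the written procedure. Section 8.5.5 treats prompt SAE notification as essential to participant safety and to the sponsor's legal duties. Section 8.7 routes protocol-defined overdoses through the same process, so they meet the same ambiguity.

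**Working it through.** No sample-size, power or error-rate figure is involved. The check is a comparison of the texts plus clock arithmetic.

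**Inputs**
- Reporting limit: 24 hours (Section 8.5.1).
- Trigger A: any unavailability of the electronic system (Section 10.3.5, electronic-tool block).
- Trigger B: unavailability for more than 24 hours (Section 10.3.5, paper-CRF block).
- Assumption: the clock starts when the site learns of the SAE. Section 8.5.1 does not state the start for an initial report. Section 10.3.4 counts from receipt of the information, but for updated SAE data.

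**Set-up**
Let hour 0 be awareness, *s* the hour at which the outage starts (negative if before awareness), and *d* its length in hours. The system returns at hour *s* + *d*. Assume the SAE has not been reported when the outage starts.

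- Under A, paper is available from hour max(0, *s*).
- Under B read alone, paper opens just after hour *s* + 24, and only if *d* > 24. Otherwise the site reports electronically at hour *s* + *d*.

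**When B alone makes a report late**
- *s* ≥ 0 and *d* > 24: paper opens after *s* + 24 ≥ 24, so the report is late.
- *s* ≥ 0 and *d* ≤ 24: the report is late if *s* + *d* > 24.
- *s* < 0: the first available route opens at *s* + 24 or sooner, which is before hour 24. The limit can be met, although the margin is short if *s* is close to 0.

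So B alone makes the report late when the outage starts at or after awareness and the system is not back by hour 24.

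**Examples**

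| Outage start *s* | Length *d* | Trigger B alone | Trigger A |
|---|---|---|---|
| 0 | more than 24 | paper just after hour 24: late | paper at hour 0, 24 hours left |
| +6 | more than 24 | paper just after 6 + 24 = 30: at least 6 hours late | paper at hour 6, 24 − 6 = 18 hours left |
| +6 | 20 | paper never triggered; system back at 6 + 20 = 26: 2 hours late | paper at hour 6, 18 hours left |
| 0 | 10 | system back at hour 10: in time | paper at hour 0, 24 hours left |
| −12 | more than 24 | paper just after −12 + 24 = 12: up to 12 hours left | paper at hour 0, 24 hours left |

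Under A the limit can be met for any outage that starts before hour 24.

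**The case against.** The strongest answer is that the protocol already contains a route that works. The electronic-tool block sends the site to paper without any wait and gives the 24-hour limit as its reason. The paper-CRF block does not confine paper to long outages, does not forbid earlier use and tells nobody to wait. Read together with Section 8.5.1, the documents give an absolute limit and a means of meeting it. Only a site that reads the paper-CRF block in isolation would be late.

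This stands as far as it goes, and it rules out three stronger readings that a reader might infer:

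- That the paper back-up becomes available only after a day's outage. The first block says otherwise.
- That sites are instructed to hold a report past the limit. No such instruction is written.
- That every SAE learned of at the start of an outage is reported late. The 10-hour outage in the table shows that it need not be.

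The exposure is also limited. Enrollment has ceased with 25 participants treated, the documents give no outage frequency, and the outage trigger no longer applies after the DCO. The Study Reference Manual, which cannot be seen here, may tell sites more.

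What the answer does not remove is the contradiction. Both sentences are complete, they set different conditions for the same form, and the block with the practical instructions carries the condition that does not fit the limit. Telephone notification does not fill the gap, because it does not replace the signed pages.

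**Conclusion.** The point holds as an internal contradiction in Section 10.3.5, with one of the two triggers incompatible with Section 8.5.1. The paper-CRF trigger, followed alone, produces a late report in a defined set of outages: those that start at or after awareness and are not over within 24 hours of it. In the worked cases the excess is 2 hours for a 20-hour outage starting at hour 6, and at least 6 hours for a longer outage starting at the same point. The number of reports affected cannot be estimated, because neither the outage frequency nor the DCO date is given.

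The conclusion on timing rests on counting from awareness, which Section 8.5.1 does not spell out. The disagreement between the two triggers does not depend on that assumption. The primary endpoint, the sample size and the planned analyses are untouched. This is a correction to safety-reporting wording that should be made.

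**What to change.** In the paper-CRF block of Section 10.3.5, delete the condition that the outage must exceed 24 hours. Both blocks would then send the site to paper whenever the electronic system is unavailable, and the limit in Section 8.5.1 could be met. Leave the rest as it is. In particular, this correction should not add a definition of when the 24-hour clock starts, because Section 8.5.1 does not contain one.

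The cost is one phrase in the protocol, a letter to sites, and any IRB/IEC notification needed. Section 10.1.1 requires prior approval for amendments that change the study design. Whether a wording correction of this kind falls under that rule is for the sponsor to determine. If the Study Reference Manual repeats the longer condition, it should be brought into line at the same time.

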10.4.2. Contraception Guidance

Male participants

- Male participants with female partners of child-bearing potential are eligible to participate if they agree to ONE of the following during the protocol-defined time frame in Section 5.1.
 - Are abstinent from penile-vaginal intercourse as their usual and preferred lifestyle (abstinent on a long term and persistent basis) and agree to remain abstinent
 - Agree to use a male condom plus an additional method of contraception with a failure rate of <1% per year as described in Table 7 when having penile-vaginal intercourse with a woman of childbearing potential
 - Men with a pregnant or breastfeeding partner must agree to remain abstinent from penile-vaginal intercourse or use a male condom during each episode of penile penetration for the duration of the study and for at least 120 days after the last dose of study treatment.

Female participants

Table 7 Highly Effective Contraceptive Methods

CONTRACEPTIVES ^a ALLOWED DURING THE STUDY INCLUDE:	
• Highly Effective Methods^b That Have Low User Dependency Failure rate of <1% per year when used consistently and correctly.	
• Implantable progestogen-only hormone contraception associated with inhibition of ovulation ^c	
• Intrauterine device (IUD)	
• Intrauterine hormone-releasing system (IUS) ^c	
• Bilateral tubal occlusion	
• Vasectomized partner 
 Note: Vasectomized partner is a highly effective contraceptive method provided that the partner is the sole sexual partner of the woman of childbearing potential and the absence of sperm has been confirmed. If not, an additional highly effective method of contraception should be used. Spermatogenesis cycle is approximately 90 days. 	
• Highly Effective Methods^b That Are User Dependent Failure rate of <1% per year when used consistently and correctly.	

Combined (estrogen- and progestogen-containing) hormonal contraception associated with inhibition of ovulation^c

 • oral • intravaginal • transdermal • injectable
Progestogen-only hormone contraception associated with inhibition of ovulation^c

 • oral • injectable

Sexual abstinence

- *Note: Sexual abstinence is considered a highly effective method only if defined as refraining from heterosexual intercourse during the entire period of risk associated with the study intervention. The reliability of sexual abstinence needs to be evaluated in relation to the duration of the study and the preferred and usual lifestyle of the participant.*

- a. Contraceptive use by men or women should be consistent with local regulations regarding the use of contraceptive methods for those participating in clinical studies.
- b. Failure rate of <1% per year when used consistently and correctly. Typical use failure rates differ from those when used consistently and correctly.
- c. If locally required, in accordance with Clinical Trial Facilitation Group (CTFG) guidelines, acceptable contraceptive methods are limited to those which inhibit ovulation as the primary mode of action.

Note: Periodic abstinence (calendar, sympto-thermal, post-ovulation methods), withdrawal (coitus interruptus), spermicides only, and lactational amenorrhea method (LAM) are not acceptable methods of contraception. Male condom and female condom should not be used together (due to risk of failure with friction)

Note: This contraceptive guidance will also apply to participants who continue to receive study intervention after the DCO date.

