The investigator reviews the medical history, menstrual history, and recent sexual activity to decrease the risk for inclusion of a female with an early undetected pregnancy.

Male participants:

- Contraceptive use by men should be consistent with local regulations regarding the methods of contraception for those participating in clinical studies.
- Male participants are eligible to participate if they agree to the following from the time of first dose of study until 125 days after the last dose of study treatment to allow for clearance of any altered sperm:
 - Refrain from donating sperm.

PLUS, either:

- Be abstinent from heterosexual intercourse as their preferred and usual lifestyle (abstinent on long term and persistent basis) and agree to remain abstinent.

OR

- Must agree to use contraception/barrier as detailed below.
- Agree to use a male condom and female partner to use an additional highly effective contraceptive method with a failure rate of <1% per year as described in [Section 10.4.2](#) when having sexual intercourse with a woman of childbearing potential who is not currently pregnant.

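### Appendix 4 sets a 120-day post-dose minimum for men with a pregnant or breastfeeding partner although its lead-in adopts the 125-day period of Section 5.1, and it leaves unclear whether a condom alone is enough when the partner is breastfeeding

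*Protocol*

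**What the plan says.** Protocol Section 5.1 (male participants) applies from the first dose "until 125 days after the last dose of study treatment to allow for clearance of any altered sperm". Besides not donating sperm, the man has two choices. One is "Be abstinent from heterosexual intercourse as their preferred and usual lifestyle". The other is "Agree to use a male condom and female partner to use an additional highly effective contraceptive method", which applies "when having sexual intercourse with a woman of childbearing potential who is not currently pregnant". Pregnancy is the only exception stated.

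Protocol Section 10.4.2 (Appendix 4) opens its list for men whose partners are of childbearing potential by requiring that they "agree to ONE of the following during the protocol-defined time frame in Section 5.1". The first item is habitual abstinence. The second is a condom plus another method with a failure rate below 1% per year. The third reads "Men with a pregnant or breastfeeding partner must agree to remain abstinent from penile-vaginal intercourse or use a male condom" at each act, "for the duration of the study and for at least 120 days after the last dose of study treatment". It names no second method and does not require abstinence to be the man's usual lifestyle.

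Section 10.4.1 defines childbearing potential: "A woman is considered fertile following menarche and until becoming post-menopausal unless permanently sterile". Breastfeeding is not among the categories that take a woman out of it. A note after Table 7 rejects lactational amenorrhea as contraception, and another extends the Appendix 4 guidance to participants treated after the data cut-off.

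**The concern.** The 120-day figure does not match the period that its own lead-in adopts. A breastfeeding partner who is not pregnant also falls under two provisions. Section 5.1 treats her like any other woman of childbearing potential, while the third item in Appendix 4 groups her with pregnant partners, for whom a second method has no purpose. A site working from the appendix could therefore give the couple an earlier stop date, and could also accept a condom as sufficient.

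Enrollment is closed, but the text is still in use. Section 6.10 allows treatment after the data cut-off, and Section 7.1 removes study-specific visits for those who stop after it. For these men the written post-dose minimum may be what sets the stop date. Embryofetal toxicity is listed as a known class risk (Section 2.2.5), so one stop date and one method standard are desirable.

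**Working it through.** The protocol derives neither number, so there is no planned figure to reproduce. The check compares the two provisions and works out when they differ.

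**Duration**

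Inputs:
- Section 5.1 period: 125 days after the last dose.
- Section 10.4.2 third item: the duration of the study and at least 120 days after the last dose.
- d: days from the man's last dose to the end of the study. The documents give no value.

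The appendix period ends at max(120, d) days after the last dose, so

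gap = max(0, 125 − max(120, d)).

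| d (days) | Appendix end | Gap |
|---|---|---|
| 0 to 120 | 120 | 125 − 120 = 5 |
| 123 | 123 | 125 − 123 = 2 |
| 125 | 125 | 0 |
| 168 (24 weeks × 7) | 168 | 0 |

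The maximum is 5 days, or 5/125 = 4% of the Section 5.1 post-dose period.

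What d is depends on what the study means here:
- *Participant level.* Section 4.1 continues long-term contacts every 12 weeks after the 12-week Safety Follow-up. A man followed to the first of these, at about day 168, has no gap. Reaching week 12 (day 84) does not by itself end his study. A gap needs either a data cut-off that falls before his day 125 (Section 8.2 then treats him as having completed) or a last dose after the cut-off with no later study visits.
- *Study level.* Section 4.7 ends the study at the last participant's last visit, and Section 8.2 keeps it open after the cut-off until all participants stop treatment. A gap then exists only for men whose last dose falls fewer than 125 days before that date.

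**Which partners**

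- *Breastfeeding, not pregnant, of childbearing potential:* Section 5.1 applies directly, and so does the third item.
- *Pregnant:* the Section 5.1 condom rule exempts her. The 120 days conflict with 125 only if the Appendix 4 lead-in governs the third item.

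**Method, for the breastfeeding partner**

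| | Section 5.1 | Section 10.4.2, third item as one option | Section 10.4.2, third item as added duty |
|---|---|---|---|
| If not abstinent | condom plus highly effective method | condom alone | condom plus second method (from item 2) |
| If abstinent | habitual | no qualifier | habitual (from item 1) |

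The first reading conflicts with Section 5.1 whatever d is. The second does not conflict at all.

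**The case against.** A reader might infer that Appendix 4 plainly permits a condom alone for breastfeeding partners, or that every such couple loses five days of protection. The documents support neither.

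On method, the third item is a full sentence with its own subject and its own obligation, whereas the first two complete the lead-in. It can fairly be read as an extra duty that leaves the second item in force, and the second item has no exception for breastfeeding. Rejecting lactational amenorrhea points the same way, as does Section 6.8.5.3, which requires highly effective contraception; Table 7 does not list the male condom. What remains is that the item is laid out under a lead-in asking for agreement to one entry, and nothing says it is additional.

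On duration, the appendix figure is a minimum that 125 days also satisfies, so a man can comply with both provisions. Section 5.1 requires all its criteria to be met, and Sections 5 and 8 rule out waivers, so the appendix cannot relax what he agreed to. This argument stands and reduces the issue to a lower floor. It does not remove it. Section 5.3 sends sites to Appendix 4, Section 5.1 points to Section 10.4.2 for methods, and the appendix text is what is extended past the data cut-off.

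It is also fair to say that the documents give no reason for 120 days, and that the sperm-clearance reason behind 125 days is stated only in Section 5.1. For pregnant partners, moving to 125 days is therefore harmonisation with the lead-in and not correction of a demonstrated error.

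**Conclusion.** The point holds as a minor inconsistency in operative reproductive-safety text, with moderate confidence. The 120-day minimum disagrees with the time frame its own lead-in adopts. The effect is at most 5 days, and zero once the study runs to 125 days or more after the man's last dose. That condition depends on whether the study is read at participant or at study level, which the text leaves open. The difference in method is conditional: it exists only if the third item is a sufficient choice in itself.

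The documents do not say how many men have a pregnant or breastfeeding partner. The number cannot exceed the 25 treated participants and may be zero. No endpoint, sample size or analysis is affected.

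**What to change.** In the third item of the Section 10.4.2 list for male participants, replace the 120-day minimum with 125 days. Add one sentence: for a breastfeeding partner of childbearing potential who is not pregnant, the item applies in addition to the Section 5.1 rule, not instead of it.

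The cost is one number and one sentence, by amendment or a clarification to sites. For participants it means at most five more days of condom use or abstinence. It adds no second-method burden beyond what Section 5.1 already asks. Section 1 requires re-consent of those who continue after the data cut-off. Whether the consent form needs the same change cannot be judged from these documents.
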